11.2 Completion of Case Report Forms (CRFs)	32
11.3 Monitoring Procedures	32
12. PUBLICATION POLICY	32
12.1 Participating Centers	32
AppendIX I.....	42

LIST OF ABBREVIATIONS AND DEFINITIONS OF TERMS

Abbreviations	
ADAS-Cog	Alzheimer's Disease Assessment Scale Cognition Plus
ADCS	Alzheimer's Disease Cooperative Study
ADL	Activities of Daily Living
ADNI	The Alzheimer's Disease Neuroimaging Initiative
ANOVA	Analysis of Variance
BDNF	Brain-Derived Neurotrophic Factor
BNT	Boston Naming Test
CCNA	Consortium in Neurodegeneration and Aging
CDR	Clinical Dementia Rating Scale
cE	Control Tone-Stretching Exercises
CERAD	Consortium to Establish a Registry for Alzheimer's Disease
CT	Cognitive Training
cCT	Control Cognitive Training
DM	2 Tasks at Once
E	Multi-Modal Exercises
FLAIR	Fluid Attenuation Inversion Recovery
fMRI	Functional MRI
GAD-7	Generalized Anxiety Disorder 7-item scale
GDS-30	Geriatric Depression Scale
IADL	Instrumental Activities of Daily Living
ICH-GCP	Harmonization Good Clinical Practice
IRB	Institutional Review Board
IU	International units
K-M	Kaplan-Meier
LORIS	Longitudinal Online Research and Imaging System
MCI	Mild Cognitive Impairment
MMSE	Mini Mental State Examination
MoCA	Montreal Cognitive Assessment
MRI	Magnetic Resonance Imaging
PARQ+	Physical Activity Readiness Questionnaire Plus
PASE	Physical Activity Scale for the Elderly
PRT	Progressive resistance training
PTH	Parathyroid hormone
RAVLT	Rey auditory verbal learning
RPE	rate of perceived exertion
RT	Reaction time
SYNERGIC	SYNchronizing Exercises, and Remedies in GaIt and Cognition
SDST	Symbol digit substitution test
SF-36	Quality of life questionnaire – short form
SPPB	Short physical performance battery

TMT	Trail making test
VBM	Voxel-Based Morphometry
WAIS	Wechsler Abbreviated Scale of Intelligence
WMHs	White Matter Hyper-intensities
VEGF	Vascular endothelial growth factor
6MWT	Six Minute Walk Test

1. INTRODUCTION

1.1 BACKGROUND

Exercises, specifically resistance and aerobic training, have been demonstrated to improve cognitive outcomes, along with improved physical capacity and mobility[1,2]. Both aerobic [3] and resistance training[4] trials of different durations have revealed impressive results, with the most consistent findings being observed after combined interventions, multimodal exercise- lasting roughly six months to one year[1]. For example, our group has recently reported that aerobic exercise improves performance on learning a new sequence of movements. Although the training benefits of progressive resistance training (PRT) have been well documented, PRT has been studied far less extensively than aerobic training in patients with Mild Cognitive Impairment (MCI).

Exercise training is beneficial for cognition even in frail older adults and in those with low mobility as has been shown by our group[4]. Exact mechanisms supporting the benefits of exercises for cognition in humans need to be further explored but numerous studies in animals and humans have demonstrated that aerobic exercise may have neuroprotective and neurorestorative effects [4,5,5,6]. The rationale of combining aerobic and progressive resistance training as a multimodal exercise intervention is supported by research that has revealed potential beneficial effects on insulin-like growth factor-1, insulin sensitivity, and anti-inflammatory and brain-derived neurotrophic factor pathways, which are related to both sarcopenia and cognitive decline[7]. In addition, multimodal exercise interventions have shown positive effects on muscle/lean mass, cognition and brain volume [8].

Similarly, cognitive training (e.g. computer based cognitive process training) has also shown positive results in improving cognition, mobility and postural control. Several recent systematic reviews on the topic[9,10] support the cognitive benefits of training and a seated dual-task cognitive training regimen designed by our group has demonstrated that this type of training can also improve balance in healthy older adults.[11] In line with exercise training, recent research on cognitive training has also supported important improvements in brain plasticity post-intervention [12,13].

In addition, vitamin D deficiency has been linked to cognitive dysfunction, dementia and mobility decline. [1,14-16] Besides its very well-known effects on muscle and bone physiology, vitamin D is considered a neurosteroid hormone which exhibits neuroprotective attributes through antioxidative mechanisms, neuronal calcium regulation, immunomodulation, enhanced nerve conduction and detoxification mechanisms.[14,17-20] Compelling evidence from animal models and epidemiological studies supports a potential beneficial role for vitamin D on cognitive function. In this trial, we will test

if vitamin D supplementation will have a synergistic effect in improving or stabilizing cognitive function in combination with exercises and cognitive training.

Mild Cognitive Impairment is thought to be the optimum stage to intervene with preventive strategies and early treatments, in fact it is estimated that one-year delay in dementia incidence could save \$109 billion over a 30 years period the Canadian Health System.[21,22] Robustly designed trials, with longitudinal follow-up, have been recommended in MCI to investigate the comparative benefits of isolated and combined physical exercises and cognitive training. To date, the effect of adding cognitive training and vitamin D to multimodal physical exercises for improving global cognition, executive function and memory in MCI has not been assessed.[23]

The proposed **SYNERGIC TRIAL (SYN)chronizing Exercises, and Remedies in GaIt and Cognition** is uniquely designed to evaluate the effect of aerobic and progressive resistance training exercises, isolated or combined with cognitive training and vitamin D supplementation, in older adults with MCI. This trial will be conducted by the Motor Exercise and Cognition Team which is part of the Canadian Consortium in Neurodegeneration and Aging (CCNA) and the Canadian Gait and Cognition Network (CGCN).

2. STUDY DESIGN AND HYPOTHESES

2.1. HYPOTHESES

2.1.a Primary Hypotheses

1. Twenty weeks (five months) of supervised multimodal exercise (aerobic and progressive resistance training) alone and/or in combination with cognitive training (CT) and/or oral vitamin D will significantly improve global cognitive function in older adults with MCI, as assessed by primary outcome **Alzheimer's Disease Assessment Scale-Cognitive subscale plus (ADAS-Cog Plus)**.
2. Multimodal exercise alone and/or in combination with CT and/or oral vitamin D would significantly improve secondary cognitive outcomes across memory, executive function, and attention, as well mobility outcomes related to falls risk and dual-task gait, and dual-task gait cost.

3. The combination of CT and oral vitamin D with multimodal exercise will be significantly superior to either intervention alone for cognitive and functional benefits, demonstrating a synergistic effect.
4. Mechanistically, our intervention will significantly improve hippocampi volume, blood biomarkers, and BDNF levels [24], and fMRI prefrontal activation in executive control dual-task condition.

2.1.b Secondary Hypotheses

1. All active training interventions will improve brain morphology and biochemistry compared with control –placebo-interventions as defined by: increased hippocampal volume (mm^3) by MRI scanning; positive localized Voxel-Based Morphometry (VBM) brain changes (z-score relative change); decreased whole brain volume of White Matter Hyper-intensities (WMHs) (mm^3); and lead to beneficial hippocampal and anterior and posterior cingulate MRS metabolite changes (% increase in N-acetylaspartate, and increase in phosphocreatine metabolites).
2. All active interventions will improve secondary cognitive outcomes, in the domains of attention, memory, fluency, and executive function, relative to the control condition, and combined training will be superior to either single intervention.
3. Multimodal exercise will preferentially decrease inflammatory markers, and increase fitness (strength and aerobic capacity), muscle strength, and functional mobility, compared to either cognitive or control condition.
4. Cognitive and physical training will produce positive effects on psychological health and quality of life (SF-36) above and beyond the non-specific effects seen after control condition.

3. DESIGN

The **SYNERGIC TRIAL** (SYNchronizing Exercises, and Remedies in GaIt and Cognition) is a Randomized, modified factorial design with parallel-groups (five arms), and double-blind study **evaluating the cognitive effect of multimodal exercises (as a main intervention) combined with and without cognitive training and vitamin D**. This is achieved using 4 arms (1 to 4) and a 5th arm is added as a control group. Figure 1 illustrates the trial design and Figure 2 summarizes the timeline of the trial consisting of an approximate 12-18 months enrolment period, and 12 months of follow-up. The trial adheres to the Consolidated Standards of Reporting Trials (CONSORT) guidelines for conducting and reporting clinical trials, as extended to non-pharmacologic interventions. Two hundred (200)

participants with Mild Cognitive Impairment (MCI), aged 60 and older will be enrolled and randomized into one of five arms.

Arm 1: **multimodal exercises + cognitive training + Vitamin D**

Arm 2: **multimodal exercises + cognitive training + placebo D**

Arm 3: **multimodal exercises+ control cognitive training + Vitamin D**

Arm 4: **multimodal exercises + control cognitive training+ placebo D;**

Arm 5: tone-stretching exercises + control cognitive training+ placebo D.

Note: in **bold** are the active interventions. Arm 5 is the arm with pure control interventions.

Figure 1 shows the flow chart of the trial. E: multimodal exercises; **CT**: cognitive training; **cE**: control tone-stretching exercises; and **cCT**: control cognitive training.

4. STUDY OUTCOMES

4.1 PRIMARY OUTCOME: Global cognition assessed using the ADAS-Cog Plus.[25]

We expect that our combined interventions, over 20 weeks, will show improvement and/or less decline in **global cognition**. We expect a three (3) point change (continuous variable) across full intervention/ control groups on the ADAS-Cog Plus scores, a value we considered clinically significant based in previous studies using the ADAS-Cog 13 items. This expected change/ improvement is similar in magnitude to the improvements seen in positive pharmacological clinical trials in dementia in the ADAS-Cog .[26] Additionally, improving in the proportion of participants, expressed as percentages per allocated groups, with abnormal ADAS-Cog Plus (dichotomous variable) after intervention will be considered success of the intervention. ADAS-Cog Plus is described in detail in Section 7. We also expect a significant statistical improvement in the overall transformed score of ADAS-Cog Plus calculated using a validated scoring system[27] Observing a statistically significant difference in this primary outcome will be considered preliminary evidence of efficacy.

4.2 SECONDARY OUTCOMES

Secondary outcomes include neuroimaging, cognitive (neuropsychological assessments), gait and mobility outcomes including incidence of fall, blood biomarkers, quality of life scorings, as described in our primary and secondary hypotheses. Secondary outcomes are described in detail in Section 7.

5. STUDY POPULATION

5.1 PARTICIPANTS, RECRUITMENT, STRATIFICATION, AND BLINDING

We will target older adults aged 60 and over with MCI. Interventions will be done across five sites: London (lead and sponsor site, target recruitment: 70 participants), Waterloo-University of Waterloo (target recruitment: 25), Waterloo-Wilfrid Laurier University (target recruitment: 20), Montreal (target recruitment: 30) and Vancouver (target recruitment: 55). Each intervention site may have more than one recruitment center. For those who are interested in participating, a consent and screening session will be arranged as described in our participant flowchart, Figure 3.

Once informed consent is obtained, we will perform the screening tests. Those who remain eligible after the screening session including the Physical Activity Readiness Questionnaire Plus (PARQ+) and who provide written recommendation from their physician or site physician indicating their appropriateness to participate in an aerobic-based exercise training program will proceed to baseline assessments. Participants will be informed that they will be randomly assigned to one of five arms by the research coordinator and will be blinded to the investigators' hypothesis as to which is the preferred intervention arm.

All groups will have an equal volume and frequency of contact with trainers over the 12 months of the study. All primary and secondary outcomes will be obtained and analyzed by blinded assessors on different days to the training programs.

5.2 INCLUSION AND EXCLUSION CRITERIA

Inclusion criteria:

Participants must meet each of the following criteria for enrolment into the study:

1. At least 60 years of age.
2. Self-reported levels of proficiency in English or French (at Montreal site only) for speaking and understanding spoken language.
3. Able to comply with scheduled visits, treatment plan, and other trial procedures.
4. Able to ambulate at least 10 m independently.
5. Having MCI defined following Albert et al.[28] criteria as:
a-Objective cognitive impairment in one of the following four cognitive domains: memory, executive function, attention, and language operationalized using one or more of the following: MoCA Test (Montreal Cognitive Assessment) with scores ranging from 13-24/30, Logical Memory below ADNI cutoffs, CERAD word list recall < 6.

b-Preserved activities of daily living operationalized as a Score >14/23 on the Lawton-Brody IADL[29] scale and confirmed by clinician's interviews.

c-Absence of dementia using criteria from the Diagnostic and Statistical Manual of Mental Disorders, Fifth Edition [30] and/or Global CDR = 0.5.

6. Having normal or corrected to normal vision in at least one eye so that they can identify symbols and stimuli presented on a computer screen in front of them.
7. Must be in sufficient health to participate in the study's aerobic-based exercise training program. This will be determined using the PARQ+ screening tool and with an evaluation by a certified exercise physiologist and/or a physician, when appropriate indicating clearance to participate in an aerobic-based exercise training program.

Exclusion criteria:

Participants who exhibit any of the following conditions are to be excluded from the study:

1. Serious underlying disease which, in the opinion of the investigator, may preclude engagement in interventions or may interfere with the participant's ability to participate fully in the study.
2. Participant with uncontrolled major depression, schizophrenia, severe anxiety and drug abuse.
3. Current parkinsonism or any neurological disorder with residual motor deficits (e.g. stroke with motor deficit), active musculoskeletal disorders (e.g. severe osteoarthritis of lower limbs) or history of knee/hip replacement affecting gait performance at clinical evaluation
4. Intention to enroll in other clinical trials during the same time period.
5. Pre-existing or current active participation in physical activity program involving aerobic or resistance training regimen in previous 6 months.
6. Taking Cognitive enhancers, Neuroleptics, Anticholinergics, or Vitamin D in doses more than 1000IU/day or equivalent.
7. Known hypercalcemia and/or disorder that is cause of hypercalcemia (e.g. hyperparathyroidism/ Paget's disease/ Sarcoidosis).
8. Known renal/kidney insufficiency.
9. Uncontrolled hypertension.
10. Uncontrolled diabetes.

5.3 SAMPLE SIZE:

Sample size calculation is based on changes in our main primary outcome: stabilization/improvement in cognition as measured using the **Alzheimer Disease Assessment Scale Cognitive Plus** (ADAS-Cog Plus). We expect a change of three (3) points on the ADAS-Cog Plus scores, a value that is considered clinically significant, and it is similar in magnitude to the improvements seen in positive pharmacological clinical trials in dementia.[26] Two previous studies testing the effect of exercises on cognition in 200 MCI participants shown a mean score of 6-7 and a standard deviation of 3 in the ADAS-Cog.[24,31] Based on these data and assuming a mean change of 3 points in the ADAS-Cog, 34 participants per arm are required to have 80% power to detect a change of three points or more on the ADAS-Cog with a 2-tailed α error of 5%, adjusted for 10 potential pairwise comparisons. We estimate a worst case scenario of 15% of dropout rate during the 20 weeks of follow up to the main endpoint. Therefore, we will aim to recruit 40 per arm for a total of 200 participants.

Sample size estimates per group for the primary outcome: change in ADAS-Cog Plus

	Type I error=0.05	Type I error=0.01	Type I error=0.001
Power=80%	34	50	59
Power=90%	51	54	70
Power=99%	68	82	102

Reference: Independent Groups - Machin D, Campbell M, Fayers, P, Pinol A (1997) Sample Size Tables for Clinical Studies Second Ed. Blackwell Science ISBN 0-86542-870-0 p. 24-25

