Six Minute Walk Test (6MWT) ^b		X	X		X
Neuroimaging (MRI)					
Blood Draw		X	X		
Falls Calendar ^c		X	X	X	X

94 ^aTesting included in the ADAS-Cog plus95 ^bThis test may be completed at the gym facility on the first day of intervention96 ^cCalendar will be given to participant to complete and will be submitted to Research Staff at exercise training97

7. Determination of Sample Size

98 Sample size calculation is based on changes in our primary outcome: global cognitive
 99 function measured using the Alzheimer Disease Assessment Scale Cognitive 13 and

100 the plus variant (ADAS-Cog 13 and plus). A target sample of 200 participants (40 per
 101 arm) was determined based on 80% power to detect either main effects or an
 102 interaction of at least a moderate (Cohen's $d \sim 0.5$)¹ effect size of changes in the ADAS-
 103 Cog-13.² The final sample size accounted for a 15% attrition.

104

105 **8. Primary Outcomes**

106 Primary outcome will be changes in cognitive function measured with the ADAS-Cog 13
 107 items (ADAS-Cog-13) and the plus variant (ADAS-Cog-plus) at endpoint, 6 Month.
 108 Improvement at endpoint in either variant is considered evidence of efficacy.

109 **8.1 Change in cognitive function on ADAS-Cog-13 at post-intervention (Month 6)**

110 The ADAS-Cog 13 consists of 13 brief cognitive tests assessing memory, language,
 111 attention, concentration and praxis. The individual tests are listed in Table 2. Scores
 112 range from 0 to 84, with higher scores indicating severe cognitive impairment.

113 **8.2 Change in cognitive function on ADAS-Cog-Plus at post-intervention (Month 6)**

114 Four additional tests focusing on executive function will be added to the ADAS-Cog 13
 115 to comprise the plus variant³ (Table 2). Scores will be transformed into an algorithm
 116 validated by Crane et al.⁴ The higher scores will indicate severe of cognitive impairment.

117
 118 Table 2. Individual tests included in the ADAS-Cog

ADAS-Cog-13	ADAS-Cog-Plus
Word recall	Word recall
Delayed word recall	Delayed word recall
Following commands	Following commands
Constructional praxis	Constructional praxis
Ideational praxis	Ideational praxis
Naming objects	Naming objects
Orientations	Orientations
Word recognition	Word recognition
Remembering instructions	Remembering instructions
Comprehension	Comprehension
Word finding	Word finding
Spoken language	Spoken language
Number cancellation	Number cancellation
	Trial Making A and B
	Digit symbol substitution

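### Protocol 5.3: the 34 per arm for 80% power does not follow from the printed inputs, two table cells fit nothing else in the table, and SAP section 7 justifies the same 200 on another basis without explanation

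*Combined protocol and SAP*

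**What the plan says.** Protocol 5.3 sizes the trial on change in ADAS-Cog Plus. Its inputs are:

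- Difference: "assuming a mean change of 3 points in the ADAS-Cog".
- Variability, from two earlier exercise studies: "a mean score of 6-7 and a standard deviation of 3 in the ADAS-Cog".
- Error rate: "with a 2-tailed α error of 5%, adjusted for 10 potential pairwise comparisons". The method of adjustment is not named here; protocol section 8 mentions both Tukey and Hochberg.
- Result: "34 participants per arm are required to have 80% power to detect a change of three points or more on the ADAS-Cog", raised to 40 per arm (200 in all) for 15% dropout.

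A three-by-three table follows, headed "Sample size estimates per group for the primary outcome: change in ADAS-Cog Plus". Its columns are Type I error 0.05, 0.01 and 0.001, and its rows are 80%, 90% and 99% power. It states no effect size, SD or adjustment.

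SAP section 7 keeps the same total but gives another reason for it: 200 participants (40 per "arm) was determined based on 80% power to detect either main effects or an" interaction of about d = 0.5 on ADAS-Cog-13, after 15% attrition. SAP 10.2 makes no adjustment for multiple comparisons.

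**The concern.** A sample-size statement should be reproducible from the inputs printed beside it, and this one is not. The table looks like its source, because its 80%/0.05 cell is also 34. But the column is labelled with the unadjusted error rate, while the text says that the error is adjusted. The SD is that of a single score, whereas the quantity being sized is a change.

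A reader of 5.3 would take it that any two arms can be compared with 80% power. A reader of the SAP would take the same 200 as giving 80% power at half that standardised effect. Without knowing which contrast each statement covers, neither reader can judge what a null result for a single arm against control would mean.

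**Working it through.** **1. The stated 34.** Inputs from 5.3: difference 3, SD 3 (d = 3/3 = 1), two-sided 0.05 over 10 comparisons (0.005 each, taking the adjustment as Bonferroni), power 80%.

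Normal approximation: n = 2(z₀.₉₉₇₅ + z₀.₈₀)²/d² = 2(2.807 + 0.842)²/1 = 26.6, so 27 per arm. The exact two-sample t calculation gives 29. Unadjusted at 0.05, the results are 16 and 17. None of these is 34.

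Power with 34 per arm at d = 1 (noncentrality √(34/2) = 4.12):

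- Bonferroni at 0.005: 88% (exact t).
- Tukey, five arms, 5 × 34 − 5 = 165 df, critical t 2.758: 91%.

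Solving the other way, 34 per arm has exactly 80% power at 0.005 when the SD is about 3.3 (exact t 3.29; normal 3.39). The dropout step reproduces: 34/0.85 = 40.

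**2. The SD.** If the SD is 3 at both visits, the SD of change is 3√(2(1 − ρ)). The documents give no ρ, so the values below are assumptions that show the range.

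| ρ (assumed) | SD of change | n per arm, 0.005, 80% power | Power at 34 per arm |
|---|---|---|---|
| 0.5 | 3.00 | 29 | 88% |
| 0.25 | 3.67 | 42 | 68% |
| 0 | 4.24 | 56 | 51% |

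**3. The table.** Taken as labelled (unadjusted), the effect implied by each cell runs from d = 0.65 to 0.80. Dividing each column's alpha by 10, as the text implies, gives (exact t):

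| Power | Type I error | Printed n | Implied d | n at d = 0.90 |
|---|---|---|---|---|
| 80% | 0.05 | 34 | 0.912 | 35 |
| 80% | 0.01 | **50** | 0.850 | 45 |
| 80% | 0.001 | 59 | 0.901 | 60 |
| 90% | 0.05 | **51** | 0.826 | 44 |
| 90% | 0.01 | 54 | 0.903 | 55 |
| 90% | 0.001 | 70 | 0.899 | 70 |
| 99% | 0.05 | 68 | 0.894 | 68 |
| 99% | 0.01 | 82 | 0.892 | 81 |
| 99% | 0.001 | 102 | 0.887 | 100 |

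Seven cells agree within 0.887 to 0.912, an SD of about 3.3 for 3 points. At the stated d = 1 the rows would read 29/37/49, 36/45/58 and 55/66/82.

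The two outliers can be confirmed without any d. In the normal formula the ratio of n at 90% power to n at 80% depends on alpha alone. In the 0.05 column it should be 1.34 unadjusted or 1.26 adjusted; the table has 51/34 = 1.50. In the 0.01 column it should be 1.27 or 1.22; the table has 54/50 = 1.08.

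**4. The SAP basis.** At d = 0.5, two-sided 0.05, unadjusted, with 34 completers per arm (noncentrality 0.5/√(1/n₁ + 1/n₂)):

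| Contrast in the SAP | n₁ v n₂ | Noncentrality | Power |
|---|---|---|---|
| Adding cognitive training, or adding vitamin D (10.2.2, 10.2.3) | 68 v 68 | 2.92 | 82% |
| Exercise v control (10.2.1) | 136 v 34 | 2.61 | 74% |
| One arm v control, including arm 1 v arm 5 (10.2, 10.2.4) | 34 v 34 | 2.06 | 53% |

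The SAP does not say which interaction it means in section 7, so I put no figure on that.

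**The case against.** The best defence is that the error is on the safe side. On the printed inputs 34 exceeds the 29 needed, so the 80% claim is met with margin. An SD near 3.3 printed as 3 would account for the 34 and for most of the table. That stands as a plausible explanation, but the documents do not state it.

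On the SD, a change SD of 3 needs only a correlation of 0.5. Protocol section 8 also plans an ANCOVA with baseline as covariate. Under the same equal-SD assumption its residual SD, 3√(1 − ρ²), cannot exceed 3. The 42 and 56 therefore apply to an unadjusted comparison of changes, which is closer to the arm-by-time contrast in SAP 10.2. So the range shows what a missing input could do; it does not show a shortfall.

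On the SAP, the contrasts differ. The protocol sizes pairwise comparisons of arms, whereas most SAP objectives pool arms. At d = 0.5 the 68 v 68 contrasts do reach 80%, and so does 160 v 40 if nobody drops out. This stands, but the SAP does not say so, and objective 4 is a single-arm contrast.

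Three stronger readings are tempting, and the documents do not support them:

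- **That the power basis is wrong, or the trial underpowered.** The printed inputs point the other way.
- **That the table is incoherent throughout, or prints two-group totals as per-group numbers.** Seven cells agree once the stated adjustment is applied. Doubling works for 34 (2 × 17) but not for 50 (2 × 26 = 52).
- **That pairwise power is very low because d = 0.5 should be put through the ten-comparison adjustment.** Neither document plans that combination.

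**Conclusion.** The point holds in a limited form. The 34 per arm cannot be reproduced from the inputs in 5.3, which give 29 (27 by normal approximation). At 34 the power for 3 points at SD 3 is about 88% to 91%, not 80%. The table matches an unstated effect of about 0.9, omits the adjustment from its labels, and has two cells (50 and 51) that no single effect size reconciles with the other seven. The SAP gives an unexplained second basis for the same 200.

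This rests on reading the adjustment as Bonferroni (Tukey does not change the conclusion) and on equal arms. The statement that the error is conservative also needs 3 to be the SD of change, or the residual SD under ANCOVA. The severity is minor to moderate: enrolment, allocation, endpoint and model are unaffected. What is at stake is whether readers can tell which comparisons the trial was sized for.

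**What to change.** No change to enrolment is needed.

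1. In 5.3, state the SD of change and the per-comparison alpha actually used. Then either give power at 34 completers per arm as about 88% to 91% for 3 points at SD 3, or give the SD (about 3.3) that makes 34 correct.
2. Delete the table, or recompute it from those inputs, labelled per arm and with the adjusted alpha.
3. Reconcile 5.3 with SAP section 7. Say which contrasts each basis covers and why d of about 0.5 replaced the 3-point difference. Give power by contrast: at d = 0.5, unadjusted, with 34 completers per arm, 82% for 68 v 68, 74% for 136 v 34 and 53% for one arm v control.

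The cost is some wording and one short table. The drawback is that stated power for single-arm contrasts at d of about 0.5, including arm 1 v arm 5, will look less favourable than 80%.
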